Study Title: Monetary Incentives to Promote Engagement with the Oklahoma Tobacco
Helpline in Counties Experiencing Persistent Poverty

NCT Number: NCT05095779

Protocol Approval Date: April 17, 2023

RESEARCH PROTOCOL

Title of Project: Monetary Incentives to Promote Engagement with the Oklahoma Tobacco Helpline in Counties Experiencing Persistent Poverty

Principal Investigator: **[name].**, Department of Family and Preventive Medicine
[name]., Department of Pediatrics

Co-Investigators: **[name]**, Department of Family and Preventive Medicine
[name]., Department of Biostatistics and Epidemiology

Abstract

Nearly 20% of all cancers and more than 80% of lung cancers in the U.S. are attributable to smoking.¹ Research has highlighted elevated cancer mortality rates in U.S. counties experiencing persistent poverty ($\geq 20\%$ living in poverty for the past 30 years).² In Oklahoma, 16 counties meet the persistent poverty criteria.² Within these counties, smoking prevalence ranges from 19% to 32%, which is higher than the national smoking prevalence rate of 14%.³ Smoking may be a primary contributor to elevated cancer mortality rates in these counties. Incentivizing treatment engagement and smoking abstinence is a promising approach for reducing smoking rates and tobacco-related cancers. The proposed pilot project is designed to evaluate the feasibility and potential efficacy of offering small financial incentives for the completion of smoking cessation counseling among Oklahoma Tobacco Helpline (OTH) callers living in persistent poverty counties (PPCs). The study will enroll 250 adults who reside in any of the 16 persistent poverty counties in Oklahoma, who are seeking smoking cessation treatment through the OTH. Participants will be randomly assigned to OTH care *or* OTH plus escalating incentives (OTH+I) for completing up to 5 counseling calls over 8 weeks. Feasibility outcomes for the incentives-based intervention will focus on counseling call completion, follow-up assessment completion, , and perceptions of the intervention. Potential effectiveness will be evaluated by comparing self-reported abstinence rates at 12 weeks post-enrollment in OTH+I relative to OTH alone.

A. Specific Aims

Aim 1. To evaluate the feasibility of offering financial incentives for tobacco helpline counseling call completions and smoking abstinence among OTH callers who reside in Oklahoma PPCs.

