Hypothesis: The feasibility of the incentives intervention will be evaluated based on several metrics including counseling call completion rates (≥ 3 completed), follow-up assessment completion rates ($\geq 75\%$), smoking cessation rates at the 12-week follow-up ($\geq 25\%$ biochemically-verified 7-day point prevalence abstinence), incentive costs, and positive perceptions of the intervention.

Aim 2. To evaluate the potential efficacy of OTH+I relative to OTH alone.

Hypothesis: Individuals randomly assigned to the OTH+I will complete more counseling calls and achieve higher rates of biochemically-verified abstinence at the 12-week follow-up than those assigned to OTH alone.

The current study will generate preliminary data for a full-scale research proposal to evaluate the impact of offering a financial incentives program for OTH callers with the goals of increasing smoking cessation treatment uptake and cessation rates in PPCs, and reducing tobacco-related cancer incidence and mortality.

Note, the original study protocol planned to gather biochemically-verified abstinence using carbon monoxide breath samples. Due to a technical difficulty, breath samples will not be gathered from participants and study staff will gather self-reported smoking status. Upon data analysis, the research team will take the above specified aims to evaluate the feasibility of and need of gathering biochemically-verified abstinence in such interventions.

B. Background and Significance

Smoking prevalence rates are disproportionately high among adults of low SES,⁴ and socioeconomic disadvantage is associated with a reduced likelihood of smoking cessation.⁵⁻¹⁰ The incidence of lung cancer, a disease primarily caused by smoking, is far greater among those with less education and those living in poverty relative to their higher socioeconomic status (SES) counterparts.^{11,12} Although individuals of lower SES are just as likely to initiate quit attempts, they are less likely to succeed.¹³ Likewise, smoking cessation interventions for low-SES adults have produced very low abstinence rates at follow-up.¹⁴⁻¹⁷ Treatment approaches are needed to target socioeconomically disadvantaged people specifically and to reduce barriers to smoking cessation.

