[name], Ph.D. (Program Co-Leader) is an Assistant Professor in the OUHSC Department of Pediatrics and Director of the OTH. [name] is an affiliate of the HPRC, and he offices at the HPRC in order to facilitate communication and collaboration between the HPRC and the OTH. [name] oversees the state helpline contract with Optum, which is the OTH operator.

[name], MD (Co-investigator) is a Professor in the Department of Family and Preventive Medicine, and Associate Director of Community Outreach and Engagement at the NCI-Designated SCC. [name] is an affiliate of the TSET HPRC, and he offices at the HPRC to facilitate communication and collaboration. [name] research focuses on rural and tribal health, including tobacco use (e.g.,⁴⁶⁻⁵⁰). He will assist with rural and tribal outreach and recruitment efforts.

[name], Ph.D. (Co-Investigator) is an Assistant Professor in the OUHSC College of Public Health, within the Department of Biostatistics and Epidemiology and a member of the TSET HPRC. She has a history of tobacco-focused and other collaborations with [name] (Program Leader).^{43, 51-55} She will provide biostatistics support for the study.

D. Research Design and Methods (What, When, How, Where)

Study Overview. The proposed randomized controlled trial will enroll 250 adults who are seeking smoking cessation treatment through the OTH and who reside in any of the 16 PPCs in Oklahoma. Participants will be randomly assigned to OTH *or* OTH plus escalating incentives (OTH+I) for completing up to 5 counseling calls over 8 weeks. Feasibility outcomes for the incentives-based intervention will focus on counseling call completion, follow-up assessment completion, smoking cessation, incentive costs, and perceptions of the intervention. Potential effectiveness will be evaluated based on comparisons of counseling call completions at 12 weeks post-enrollment (4 weeks after incentives have ended) in OTH+I relative to OTH alone.

Randomization Plan. Randomization will be stratified by sex (male vs. female), race/ethnicity (White vs. non-White), and cigarettes smoked per day (≤ 10 vs. > 10).

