Interventions. Eligible OTH callers will be randomly assigned to one of two treatment groups: OTH or OTH+I. OTH care will include up to 5 counseling calls with a Tobacco Treatment Specialist and eight weeks of NRT. Note that an additional 6 weeks supply of NRT will be provided beyond the 2-week supply typically offered by the OTH to ensure that all participants receive adequate pharmacotherapy. OTH+I will include all components of OTH care plus escalating incentives for completing up to 5 counseling calls over 8 weeks (at least one week apart). Based on the incentive schedule used in our current (PI: [name], R01CA197314) and past research,^{29,30} incentives will start at \$20 for completing the first call, and will increase by \$5 for each consecutive call completed until the 5th call is completed (i.e., up to \$40 may be earned for completing the 5th call). The incentive will reset to \$20 if a call is missed (i.e., not completed within 2 weeks of the prior call). OTH treatment group participants may receive up to \$140 and OTH+I treatment group participants may receive up to \$290.

Contingency Management (CM). CM participants will receive counseling and nicotine replacement therapy (as described above). They will receive financial incentives for completing counseling calls.

Measurement of Abstinence.

Participants enrolled prior to May 19, 2022 who self-report smoking abstinence at 8 weeks post enrollment will receive the abstinence payment of \$50 as specified in the initial study application. Because breath samples will not be gathered as specified in the initial protocol, these participants may not receive the \$20 breath sample payments. Participants who are enrolled after May 19, 2022 will follow the payment schedule as outlined above in the protocol (payments for questionnaires, incentive group will also receive payments for counseling calls), and the payments for breath samples will be removed. In total, the standard care group will be eligible for up to \$140. In total, the standard care plus financial incentives group will be eligible for \$290.

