Measures. Participants will be asked to complete a web-based Research Electronic Data Capture (REDCap)^{56,57} assessment upon enrollment to assess sociodemographic characteristics and tobacco use history, and again at 4-, 8- and 12-weeks post-enrollment to assess self-reported smoking status and perceptions of the intervention. Participants will be compensated \$50 for the baseline assessment and \$30 for each of the following assessments. The number of completed counseling sessions will be documented (data provided by Optum), as well as follow-up completion rates at 8- and 12- weeks post-enrollment. Participants will be compensated via Greenphire reloadable study credit card.

Data Loss Prevention. Phones will be programmed to connect to our secure server 4 times daily to upload encrypted data, to overcome the potential loss of data if participants lose or change phones, which has rarely occurred in our previous research. This strategy will also allow the staff to monitor participant survey completion rates and call participants when this rate is low. Importantly, assessment data are password protected and encrypted. Thus, study data are only accessible by the research team. Data will be remotely deleted from lost phones and one replacement phone will be provided.

Disclosure of Results to Participants. Study results will not be disclosed to participants.

Future Use of Data. Identifiers might be removed and the de-identified information may be used for future research without additional informed consent from the subject.

E. Chart Review

This protocol does not involve a chart review. However, please note that participants will be required to disclose some sociodemographic information and tobacco history to determine eligibility and to identify differences between eligible and ineligible participants including address, age, phone, sex, ethnicity, race, and ethnicity. All information will be stored in a REDCap database.

F. Biospecimens

No biospecimens will be collected as part of this protocol.

G. Banking/Repository/Database

Questionnaire and expired carbon monoxide, will be collected and stored via REDCap and the INSIGHT mobile health platform. No biospecimens will be stored.

H. Inclusion / Exclusion Criteria

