
Data collection will occur remotely via telephone, and web- and smartphone-based surveys from the OTH and the OUHSC.

M. Statistical Methods

In our previous research, smoking abstinence rates were 14% vs. 33% for SC (counseling + pharmacotherapy) and SC plus incentives, respectively, at the 12 week post-quit-date follow-up in safety net hospital patients,¹⁴ and preliminary findings are similar at 12 weeks post-quit-date (13% vs. 35%, N=235) in our ongoing randomized controlled trial (PI: [name]; R01CA197314). Assuming a two-sided alpha of 0.05, a sample of 250 participants (80 per group) will offer 80% power to detect an 18% difference in cessation rates between OTH and OTH+I at the 12-week follow-up if we assume abstinence rates of 12% vs. 30%. This sample size would also offer 80% power to detect a small effect size of intervention group (OTH vs. OTH+I) on the number of counseling calls completed (0-5 calls possible).

Feasibility (Aim 1). The feasibility of offering treatment-related incentives via the OTH will be evaluated based on several metrics including the total number of counseling calls completed (0-5 possible), with the goal of achieving an average ≥ 3 completed counseling calls, and a follow-up rate of $\geq 75\%$ based on follow-up rates in our previous³⁰ and ongoing trial (PI: [name]; R01CA197314). As in other CM studies,^{60,62,66,67,68} an intent-to-treat approach will be used in which participants who do not demonstrate biochemical verification of abstinence will be classified as smoking (i.e., *no need to account for loss to follow-up*). We will characterize intent-to-treat smoking cessation rates at the 12-week follow-up, with the goal of achieving $\geq 25\%$ biochemically-verified 7-day point prevalence abstinence in the incentives group. Participant perceptions of the intervention will be characterized, as well as the costs associated with counseling- and abstinence-contingent incentives.

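### The sample-size statement gives 250 participants but 80 per group in a two-arm trial; its 80% power belongs to 160, and its power claim for counseling calls rests on an undefined "small" effect

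*Combined protocol and SAP*

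**What the plan says.** The enrolment target is the same in the Abstract ("The study will enroll 250 adults who reside in any of the 16 persistent poverty counties in Oklahoma") and in Section D, Study Overview ("The proposed randomized controlled trial will enroll 250 adults"). Section D, Interventions, sets out a two-arm design: "Eligible OTH callers will be randomly assigned to one of two treatment groups: OTH or OTH+I". No allocation ratio is stated; the Randomization Plan lists only stratification factors.

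The power statement is in Section M, for a two-sided alpha of 0.05 and 12-week abstinence of 12% against 30%: "a sample of 250 participants (80 per group) will offer 80% power to detect an 18% difference in cessation rates". The sentence after it carries the claim over to the number of counseling calls (0 to 5): "This sample size would also offer 80% power to detect a small effect size of intervention group". It gives no standardised difference, SD or test.

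The planned analyses are logistic regression for abstinence, which Section M names as the primary outcome, and linear regression for calls, with count models as a fallback. Calls also appear in the Aim 2 hypothesis: "Individuals randomly assigned to the OTH+I will complete more counseling calls and achieve higher rates of biochemically-verified abstinence".

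**The concern.** Total, group size and power cannot all be right in one sentence. The enrolment target itself is clear. What a reader cannot tell is whether the power calculation describes 160 analysed out of 250, or was made for 160 and never updated.

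For abstinence the stake is small: the stated power is either right (160 analysed) or too low (250 analysed). The calls sentence is different. It relies on the same ambiguous sample size and promises 80% power for an effect described only as small. If small is read in a conventional way, the claim is too optimistic at either size. A non-significant difference in calls could then be taken to rule out a small effect that the trial had little chance of finding, in a pilot meant to inform a full-scale proposal.

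**Working it through.** **Inputs.** From Section M: two-sided alpha 0.05 (z = 1.960), 80% power (z = 0.842), p1 = 0.12, p2 = 0.30, 80 per group, total 250. From Section D: two arms. Assumption: 1:1 allocation, which the single per-group figure implies.

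**1. The totals.** 2 × 80 = 160. 250 / 2 = 125 per group.

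**2. Reproducing the plan's 80%.** With p̄ = (0.12 + 0.30)/2 = 0.21, the pooled two-proportion formula is

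n = [1.960·√(2·0.21·0.79) + 0.842·√(0.12·0.88 + 0.30·0.70)]² / 0.18²
 = [1.960·0.5760 + 0.842·0.5618]² / 0.0324 = 79.2, rounded up to **80 per group**.

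Power = Φ[(0.18 − 1.960·SE0)/SE1], where SE0 = 0.5760/√n and SE1 = 0.5618/√n.

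- n = 80: SE0 = 0.0644, SE1 = 0.0628, Φ(0.856) = **80.4%**. This is the plan's figure.
- n = 125: SE0 = 0.0515, SE1 = 0.0502, Φ(1.573) = **94.2%**.

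The choice of method does not change the picture. Across pooled, unpooled, arcsine, log-odds Wald, continuity-corrected, exact chi-square and Fisher calculations, power runs from 74% to 82% at 80 per group and from 92% to 95% at 125. The log-odds Wald test, closest to the planned logistic regression, gives 77.5% and 92.4% by its large-sample formula. The per-group size for 80% power is 77 to 90 across the closed-form methods; none comes near 125.

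At 125 per group, 80% power is reached at 12% against about 26% (25.6% to 26.7% by method).

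**3. Can anything in the document link 160 to 250?**

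- *Attrition.* Going from 250 to 160 means losing 1 − 160/250 = 36%. The plan's follow-up goal is at least 75%, which leaves 125 × 0.75 ≈ 94 per group, not 80. In the other direction, 80/0.75 = 106.7, so 107 per group or 214 in total. Section M also says that loss to follow-up needs no allowance, because participants without verified abstinence count as smoking.
- *Unequal allocation.* None is stated. An 80/170 split would give 90.5% or 91.6% (pooled), depending on which arm is larger, not 80%.
- *Third arm.* There is none.
- *For calls,* survey dropout is not an explanation, because Section D, Measures, takes the counts from the helpline operator.

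**4. Counseling calls.** For a two-sample comparison of means, the detectable standardised difference is about (1.960 + 0.842)·√(2/n). This gives 0.443 at n = 80 and 0.354 at n = 125. The t-based values are **0.45 SD** and **0.36 SD**.

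Power by meaning of small (t-test, two-sided 0.05):

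| Small means | 80 per group | 125 per group |
|---|---|---|
| 0.2 SD | 24% | 35% |
| 0.28 SD (f² = 0.02 in linear regression; 2·√0.02) | 43% | 61% |
| 0.3 SD | 47% | 66% |
| 0.4 SD | 71% | 88% |

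For 0.2 SD, 80% power needs about 2·(2.802/0.2)² = 392.4, so 393 per group (394 with the t distribution). Covariate adjustment would have to explain 1 − (0.2/0.356)² = 68% of the variance in calls at 125 per group, or 1 − (0.2/0.446)² = 80% at 80, to bring 0.2 SD up to 80% power.

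**The case against.** Four points can be made in the plan's favour.

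- *The enrolment target is not in doubt.* It is 250 in three places, and 160 appears nowhere. This stands: the conflict lies in the per-group figure and the power attached to it, not in how many people to recruit.
- *The primary outcome is not at risk, and this is a pilot.* This stands too. It lowers the weight of the point, but it does not make the sentence correct, and the protocol chose to make formal power claims.
- *The calls criticism depends on what small means.* It does. The document does not say, and 0.2 SD is an outside convention. The t-test is also only an approximation for a 0-to-5 count that may be analysed with covariates or a count model. What survives is that the claim cannot be checked as written, and that it holds only if small means about 0.36 SD or more (125 per group) or 0.45 SD or more (80 per group). How central calls are is itself unsettled: Study Overview says "Potential effectiveness will be evaluated based on comparisons of counseling call completions at 12 weeks post-enrollment", while the Abstract judges potential effectiveness on self-reported abstinence. The Aim 2 hypothesis is enough to make calls matter.
- *The 94% has conditions of its own.* The preliminary ongoing-trial rates cited in support of the planning assumption (13% against 35%) are described in Section B as biochemically verified, and the outcome is now self-report. If both assumed rates rose by 8 points (20% against 38%, an illustration), pooled power at 125 per group would be 88%. If only the 75% followed up were analysed (about 94 per group), 12% against 30% would give 86%. Any replacement text should state these conditions.

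**Conclusion.** The point holds. The sample-size sentence is internally inconsistent, and nothing in the document reconciles it.

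For abstinence, the stated 80% is right for 160 analysed. It is too low for 250, where power is about 94% (92% to 95% by method). That figure assumes 1:1 allocation, the plan's 12% and 30%, and all participants kept in the denominator with missing counted as smoking. That last rule is worded through biochemical verification, so carrying it over to self-report is an assumption.

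For calls, the 80% claim is unsupported because the effect is undefined. At 0.2 SD, power is about 24% (80 per group) or 35% (125); at 0.28 SD it is 43% or 61%.

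This should be corrected, but it does not threaten the validity of the trial.

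**What to change.** Revise two sentences in Section M.

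1. **Abstinence.** State total N, allocation ratio, number per group and the matching power together.
   - If 250 at 1:1 is intended: 125 per group gives about 94% power for 12% against 30%, and 80% power for 12% against about 26%, with everyone randomised analysed and missing smoking status counted as smoking. Restate that missing-data rule for self-report, and say whether 12% and 30% are still the expected rates under self-report.
   - If 80 per group is the intended analysed size: state the retention this implies (80/125 = 64%) and reconcile it with the intent-to-treat rule and the 75% follow-up goal.
2. **Counseling calls.** Replace the reference to a small effect with the standardised difference detectable at 80% power (0.36 SD at 125 per group, 0.45 SD at 80), and name the test the power refers to.

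The cost is an edit to the text. Enrolment and procedures are unaffected if 250 is the intended total.

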Potential Efficacy (Aim 2). Logistic regression analyses will be conducted to evaluate the influence of OTH vs. OTH+I on biochemically-confirmed 7-day point prevalence smoking abstinence (binary) at 12 weeks (primary outcome) post-enrollment which is 4 weeks after incentives have ended. Linear regression analyses will be conducted to evaluate the influence of treatment group on the number of counseling calls completed. However, if the number of counseling calls completed is not normally distributed, we will explore the use of other models such as Poisson, negative binomial, or zero-inflated models. Covariates in the analyses may include age, sex, race/ethnicity, nicotine dependence, insurance status, annual household income, and/or educational attainment.

Note, the original study protocol planned to gather biochemically-verified abstinence using carbon monoxide breath samples. Due to a technical difficulty, breath samples will not be gathered from participants and study staff will gather self-reported smoking status. Upon data analysis, the research team will take the above specified aims to evaluate the feasibility of and need of gathering biochemically-verified abstinence in such interventions.

N. Data and Safety Monitoring Plan

The Program Leaders ([name], [name]) will be responsible for all data monitoring and for compliance with all federal and OUHSC IRB policies and procedures for monitoring progress, safety, reporting of unanticipated problems or adverse events, and assuring actions resulting in suspension of the study are reported.

Because this proposal reflects a pilot/feasibility study, a formal Data Safety and Monitoring Board (DSMB) is not required. The program leaders will be responsible for monitoring rates of enrollment, risks of participation, protocol adherence by the research team, safety and confidentiality of data collection, data entry, and statistical issues. Relevant unanticipated problems, adverse events, or participant concerns will be reviewed by the program leaders. The OUHSC IRB will be informed of any findings. All modifications to the protocol will be submitted for IRB approval. Changes to or errors in the protocol will be promptly disseminated to study personnel via e-mail, and retraining procedures will be implemented as needed. Appropriate modifications will be made in consultation with the designated program person at the National Institutes of Health if necessary.

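### The claim of 80% power for a 'small' effect on counseling calls defines no effect; the detectable standardised difference is 0.36 (125 per group) or 0.45 (80 per group), above the usual small benchmarks

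*Combined protocol and SAP*

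**What the plan says.** The power paragraph of section M makes two claims. The first concerns abstinence: "a sample of 250 participants (80 per group) will offer 80% power to detect an 18% difference in cessation rates", for assumed rates of 12% and 30% at a two-sided alpha of 0.05. The second concerns calls, on a scale of 0 to 5: "This sample size would also offer 80% power to detect a small effect size of intervention group (OTH vs. OTH+I"). For calls the paragraph states no standardised difference, variance explained, rate ratio, expected mean, SD or difference in calls.

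The analysis is described under Potential Efficacy (Aim 2) in section M: "Linear regression analyses will be conducted to evaluate the influence of treatment group on the number of counseling calls completed". If the counts are not normally distributed, "we will explore the use of other models such as Poisson, negative binomial, or zero-inflated models". Covariates are optional, and no variance explained by them is assumed.

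On the standing of the outcome, the same subsection labels as primary "smoking abstinence (binary) at 12 weeks (primary outcome) post-enrollment which is 4 weeks after incentives have ended", and the Abstract agrees: "Potential effectiveness will be evaluated by comparing self-reported abstinence rates at 12 weeks post-enrollment in OTH+I relative to OTH alone". Calls nevertheless appear in the Aim 2 hypothesis in section A: "Individuals randomly assigned to the OTH+I will complete more counseling calls and achieve higher rates of biochemically-verified abstinence". The Study Overview in section D goes further and names call completion as the comparison by which potential effectiveness will be judged.

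**The concern.** A power statement needs an effect, a sample size, an alpha and a model. Here the effect is a single adjective. The sample size is also unclear, because two arms of 80 make 160, not 250. The abstinence claim just before it does state its effect, so the paragraph does not hold the calls claim to the same standard.

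On the benchmarks usually attached to the word 'small', two groups of 80 to 125 look too few for 80% power. If so, the plan promises more sensitivity than the design has, on the behavior that the incentives pay for. Section A says of the study's purpose: "The current study will generate preliminary data for a full-scale research proposal". A reader of that proposal who accepted the 80% could take a null result on calls as evidence against small effects that this trial would more often than not miss.

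**Working it through.** **Inputs from section M.** Two-sided alpha 0.05, stated for abstinence and taken to carry over to calls; power 80%; 250 participants in total, or 80 per group; two arms; linear regression of calls on group.

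**Assumed inputs.** 1:1 allocation, so n = 125 or 80 per group. Benchmarks for 'small': d = 0.20, or f-squared = 0.02, which for two equal groups is d = 2 × √0.02 = 0.283. Neither benchmark is in the documents.

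**Step 1: the plan's reproducible figure.** For 12% against 30%, the pooled rate is 0.21 and

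n per group = [1.960 × √(2 × 0.21 × 0.79) + 0.842 × √(0.12 × 0.88 + 0.30 × 0.70)]² / 0.18² = 79.2, rounded up to 80.

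Power is 80.4% with 80 per group and 94.2% with 125. So 80 per group is the number behind the stated 80% for abstinence.

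**Step 2: detectable effect for calls.** With one binary predictor, the linear regression test is the two-sample t-test. The normal approximation is d = (1.960 + 0.842) × √(2/n):

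- n = 125: 2.802 × √0.016 = 0.354
- n = 80: 2.802 × √0.025 = 0.443

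The noncentral t (df = 2n − 2, noncentrality d × √(n/2)) gives slightly larger values. With f-squared = d²/4 and R² = f-squared/(1 + f-squared):

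| n per group | Detectable d | f-squared | R² |
|---|---|---|---|
| 125 | 0.356 | 0.032 | 0.031 |
| 80 | 0.446 | 0.050 | 0.047 |

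**Step 3: power if 'small' means a given d** (noncentral t, two-sided 0.05), and the number per group needed for 80%:

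| d | Power, 125 per group | Power, 80 per group | n per group for 80% |
|---|---|---|---|
| 0.20 | 35.0% | 24.2% | 394 |
| 0.283 (f-squared 0.02) | 60.5% | 42.8% | 198 |
| 0.30 | 65.6% | 47.1% | 176 |
| 0.35 | 78.7% | 59.5% | 130 |
| 0.40 | 88.3% | 71.0% | 100 |

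**Step 4: could another choice recover 80% at the benchmarks?**

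- *One-sided 0.05*, contrary to the stated two-sided alpha. The best case (d = 0.283, 125 per group) reaches 72.1%.
- *Covariate adjustment.* The required R² is 1 − (d / detectable d)². With 125 per group, covariates would have to explain about 36% of the variance at d = 0.283 or 68% at d = 0.20. With 80 per group the figures are 59% and 80%. The plan assumes none.
- *Count models.* Their power cannot be derived from the documents, which give no control mean, dispersion or zero fraction. A simulation of Poisson regression with robust variance on 0–5 counts (assumed control mean 1.5–3.0, SD 1.5–2.0) gave power close to Step 3. At d = 0.20 it was 34–36% (125 per group) and 22–25% (80 per group). At d = 0.283 it was 59–61% and 40–43%. Negative binomial and zero-inflated models were not tested.

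**Step 5: in calls.** The difference is d × SD. For an assumed SD of 1.5 to 2.0, the detectable difference is 0.53 to 0.71 calls with 125 per group, or 0.67 to 0.89 with 80.

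**The case against.** The strongest reply is that the plan never ties 'small' to a number, so no figure in it contradicts the 80%. The shortfall appears only after an outside convention is supplied. If 'small' means a band running up toward d = 0.5, both 0.36 and 0.45 fall inside it, and each sample size has 80% power for some effect that could be called small. On this view the gap is a missing specification and not an arithmetic error. The statement is also secondary, the study is a pilot with abstinence labeled primary, and the Aim 1 target for calls (an average of at least 3) does not depend on it.

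Part of this stands. The benchmarks are assumptions, and the shortfall must be stated as conditional on them. The statement is secondary and did not set the sample size. The figures in calls and the Poisson check also rest on assumed means and SDs, so they are illustrative only.

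The rest does not clear the sentence. The band reading is equally an assumption, and at its lower end power is 24% to 35%. With the 80 per group that reproduces the abstinence calculation, even d = 0.40 has only 71% power. On any reading, the plan does not tell the reader what difference in calls it could detect.

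**Conclusion.** The concern holds. The 80% cannot be reproduced, because the effect it refers to is undefined, and it is not reached at either usual benchmark. For the planned linear model the trial has 80% power for d = 0.36 with 125 per group or d = 0.45 with 80 per group, about 3% or 5% of the variance in calls. At the benchmarks, power is between 24% and 61%, depending on the benchmark and on the number per group.

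The detectable values assume 1:1 allocation, two-sided alpha 0.05 and no covariate adjustment. The shortfall also depends on what 'small' means: with 125 per group the sentence becomes true from about d = 0.36 upward, and with 80 per group from about 0.45. This should be fixed. It does not affect the calculation for the outcome labeled primary.

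**What to change.** First settle whether 250 in total or 80 per group applies; that conflict is a separate point. Then replace the wording on a small effect with the metric and value. For example: *With 125 per group, the trial has 80% power (two-sided alpha 0.05, linear model) to detect a standardised difference of 0.36 in the number of counseling calls completed.* Use 0.45 if 80 per group applies. If a difference in calls is added, give the SD and its source, or label the SD as assumed.

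The cost is one sentence and a less favorable stated figure for an outcome that section M does not label primary. No change to the design or the analysis is needed.
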